6.2 SUBJECT ACCRUAL

We will attempt to enroll up to 41 patients per group. Patients who complete the WL arm of the study will cross-over to the ACT arm. To provide for patients who enroll but then drop out before completing all follow-up measures, we will attempt to enroll up to 90 patients total. As of January 2015, approximately 70 of the patients enrolled on the NF1 Natural History study (08-C-0079) are within the eligible age range of the study, and are not on a MEK inhibitor trial (or planning to start one in the next six months). In addition, about 300 individuals are signed up on the CTF registry and are within the study's age range and have a PN. We will email these individuals as another recruitment source (see Appendices S & T for emails). Additionally, we will send email fliers to other NF clinics in the U.S. that see patients within this study's age range (e.g., Johns Hopkins, University of Chicago, Massachusetts General Hospital, etc.). The flier is in [Appendix W](#). If 5 – 6 patients per month are entered onto this intervention study, data collection could be completed within 30 months. Given that external funding will provide a full-term postdoctoral fellow who will help with scheduling and will conduct the majority of the ACT treatment sessions, this is presumed to be a reasonable goal.

7 HUMAN SUBJECTS PROTECTIONS

7.1 RATIONALE FOR SUBJECT SELECTION

Neurofibromatosis type 1 is a genetic disorder with a worldwide incidence of 1:3500 individuals. No groups, in regards to gender, race or ethnicity, are being excluded from participation in the trial. Because the research on the effectiveness of ACT with younger adolescents is still emerging, children 15 and younger will be excluded from the present study.

7.2 PARTICIPATION OF CHILDREN

Children 16-17 years of age will be entered onto this research trial. Children will be evaluated by clinicians trained in pediatrics, and will be cared for in the pediatric clinic or outpatient setting. Some of the participants will be co-enrolled on [name] NCI protocol 08-C-0079 (Natural History Study and Longitudinal Assessment of Children, Adolescents, and Adults with Neurofibromatosis Type 1), where the physical needs of participants will be addressed. If patients require hospital admission, they will be cared for on the pediatric unit of the CRC by the POB staff or on the adult unit of the CRC, depending on age.

7.3 PARTICIPATION OF SUBJECTS UNABLE TO GIVE CONSENT

Subjects unable to give consent are excluded from enrolling in the protocol. Should the subject become decisionally impaired during participation he/she will be removed from study as they will no longer be capable of completing the research interventions.

7.4 EVALUATION OF BENEFITS AND RISKS/DISCOMFORTS.

As this is a behavioral intervention study, no medical treatments will be administered and therefore the risks are considered minimal. The completion of questionnaires requires a maximum of 35 minutes at baseline and follow-up time points. Although we do not anticipate this, one potential risk of participation is significantly increased levels of anxiety related to the sessions, such as discussing the impact of pain on quality of life and the time involved in completing exercises at home. The study's PI ([name]) and the other trainers will be closely monitoring patients for any such distress. They are prepared to address any signs or symptoms of anxiety or emotional distress that occur throughout the sessions. Also, if patients endorse a significant level of depression on the CES-D, defined as a raw score of 27 or higher (Geisser, Roth, & Robinson, 1997), [name] or another trainer under [name] supervision will be available to respond (this form will be checked within 24 hours of completion and before the patient leaves the NIH). Responses could include discussing these concerns with the participant, referral for a psychiatry consult while at the NIH, and/or providing referrals for therapeutic services in the participant's local area beyond the scope of the intervention. Any services provided at the NIH in response to an urgent psychological problem that occurs during the workshop will be at no cost to the participant. While this is not anticipated to be necessary, if it is judged to be in the best interest of the participant to stop the study sessions prematurely, this will be done. Another small risk is involved with electrocardiogram, in that the person may develop a mild rash where the electrodes were attached. This is rare, and the rash often goes away without treatment.

The research on ACT to date indicates that it is at least as helpful as standard care and other methodologies (e.g., traditional cognitive-behavioral therapy, relaxation training) for individuals with various types of pain, and more effective than treatment as usual or inactive control groups. Thus, there is the potential for direct benefit to participants.

For participants who are 16-17, this research does not involve greater than minimal risk, and participants in this age group will be provided with the opportunity to assent to participate. Hence this study meets the requirements of 45 CFR 46.404 in that it does not involve greater than minimal risk, but there may also be the potential for direct benefit from participation.

7.5 CONSENT AND ASSENT PROCESS AND DOCUMENTATION

The questionnaires and training sessions involved in this study and the attendant risks, discomforts and benefits of these processes, will be carefully explained to the patient and the patient's parents or guardian if he/she is a minor. All family members who are present will be given the opportunity to ask questions. Patients (and parents in the case of minors) will be given the opportunity to discuss their decision privately for as long as they request, either in the clinic room or in a location of their choice. A signed informed consent document will be obtained prior to entry onto the study and completion of baseline questionnaires. Written consent or assent for children 16-17 years of age for participation in this study will be obtained by the principal investigator or an associate investigator.

For adolescent participants (ages 16-17 years), the investigators are requesting a waiver from the IRB to allow only one parent to sign the informed consent for protocol entry. Because many patients must travel to the NIH from long distances at substantial expense, requiring both parents to be present for the consent process could be a financial hardship for many families. The PI or

an associate investigator will obtain consent in all cases. When guardianship status of the child is uncertain, documentation of custody status must be obtained.

In situations where there is joint custody of a child, both parents must sign consent. If only one parent can be present at NIH, the other parent's consent can be obtained by telephone via the procedure described in section **7.5.3**.

Where deemed appropriate by the clinician and the adolescent's parent(s) or guardian, the adolescent will also be included in all discussions about the trial and age-appropriate language will be used to describe the procedures and tests involved in this study, along with the risks, discomforts and benefits of participation. Adolescents under the age of 18, but who are age ≥ 16 or older will be asked to sign an age appropriate assent form. The consent/assent process will be documented in the adolescent's medical record, including the assessment of the adolescent's ability to provide assent (verbal versus written) as applicable.

7.5.1 Request for waiver of consent for screening evaluation

Although consent will be obtained prior to enrollment on this study, a waiver is requested for obtaining informed consent to send recruitment e-mails and to conduct initial screening questions over the phone. According to OHRP, "In order to permit investigators to obtain and record identifiable private information for the purposes of identifying potential subjects, OHRP expects that IRBs routinely will waive the requirement for informed consent for such activities. In assessing the level of risk to determine whether a waiver of informed consent or parental permission is permissible for the identification of potential subjects, the IRB need only consider the risk of investigators accessing the subjects' identifiable private information, not the risks of the research in toto. (From Frequently asked questions from OHRP: <http://answers.hhs.gov/ohrp/categories/1566>).

7.5.2 Consent for minors when they reach the age of majority

When a pediatric subject reaches age 18, continued participation (including ongoing interactions with the subject or continued analysis of identifiable data) will require consenting of the now adult with the standard protocol consent document to ensure legally effective informed consent has been obtained. Given the length of time that has transpired for some of the subjects since their last visit for this study, we request waiver of informed consent for those individuals who have completed their participation in the research study.

Requirements for Waiver of Consent consistent with 45 CFR 46.116 (d):

- (1) The research involves no more than minimal risk to the subjects.
 - a. Analysis of samples and data from this study involves no additional risks to subjects.
- (2) The waiver or alteration will not adversely affect the rights and welfare of the subjects.
 - a. Retention of these samples or data does not affect the welfare of subjects.
- (3) The research could not practicably be carried out without the waiver or alteration.
 - a. Considering the length of time between a minor's enrollment and their age of majority, it is possible that more than a few subjects may be lost to follow

up. A significant reduction in the number of samples analyzed could impact the quality of the research.

(4) Whenever appropriate, the subjects will be provided with additional pertinent information after participation.

- a. We only plan to request a waiver of consent for those subjects who have been lost to follow-up or who, prior to the approval of Amendment D, have been taken off study prior to reaching the age of majority.

7.5.3 Telephone consent

The informed consent document will be sent to the subject. An explanation of the study will be provided over the telephone after the subject has had the opportunity to read the consent form. The subject will sign and date the informed consent.

The original informed consent document will be sent back to the consenting investigator who will sign and date the consent form with the date the consent was obtained via telephone.

A fully executed copy will be returned via mail for the subject's records.

The informed consent process will be documented on a progress note by the consenting investigator.

7.5.4 Telephone assent

The informed consent and assent documents will be sent to the parents/guardian and child. An explanation of the study will be provided over the telephone after the parents/guardian and child have had the opportunity to read the documents. Age-appropriate language will be used to discuss the study with the child. The parents/guardian will sign and date the informed consent, including the line for verbal assent of a child if appropriate. If an assent form is used (see above for when an assent form will be used), the child will sign and date that form.

The original signed informed consent and assent documents will be sent back to the consenting investigator who will sign and date the consent form with the date the consent was obtained via telephone.

A fully executed copy will be returned via mail to the subject.

The informed consent and assent process will be documented on a progress note by the consenting investigator.

9 APPENDICES

9.1 APPENDIX A: SCREENING PHONE CALLS TO DETERMINE ELIGIBILITY

I) Introduction

- Hi, this is _____ calling from the NIH. I'm calling to tell you about a study we are conducting for people with NF1 and plexiform tumors who have chronic pain. Do you have a few minutes now to hear about the study?

II) ACT

- The study is investigating something called Acceptance and Commitment Training, or ACT. ACT is a type of therapy that focuses on things like values and living in the present moment. It has been found to be effective in helping people with other medical conditions cope with their pain, and we have a small amount of data in adolescents with NF1 that suggests it is helpful in reducing the amount that pain interferes with the person's life. The study would involve coming to the NIH two or three times over the course of a few months, and will also involve doing some of techniques in your day-to-day life at home. We are hoping that the ACT training will help people cope with their pain so that it has less impact on their life, and that it will improve people's quality of life. To thank participants for their time, we will be providing \$30 each time you complete a set of baseline or follow-up questionnaires. You would get the money by check or direct deposit. Do you think you might be interested in hearing more about the study?
- If no: Thank you for your time.
- If yes: Okay, before I go into too much detail, let me ask you a few questions to see if you're eligible. This should take less than five minutes. If you want, I can email you these questions to read along with me. Would you prefer that? [If yes, email the questions and resume the call when they receive it.]

III) Screening

I'm going to ask you six questions about your pain. On a scale of 0 to 6, where 0 means not at all and 6 means completely, please think about the following questions:

| Has your pain: | Not at | | Some | | Com- | |
|---|--------|---|------|---|--------|---|
| | all | | | | letely | |
| 1. made it difficult for you to do work (in or outside the home)? | 0 | 1 | 2 | 3 | 4 | 5 |
| 2. made it difficult for you to do activities outside of work (leisure activities)? | 0 | 1 | 2 | 3 | 4 | 5 |
| 3. made it difficult for you to spend time with friends and family members? | 0 | 1 | 2 | 3 | 4 | 6 |

| | | | | | | | |
|---|---|---|---|---|---|---|---|
| 4. affected your mood? | 0 | 1 | 2 | 3 | 4 | 5 | 6 |
| 5. affected your ability to do physical activities (like run, walk up stairs, play sports, do chores)? | 0 | 1 | 2 | 3 | 4 | 5 | 6 |
| 6. affected your sleep? | 0 | 1 | 2 | 3 | 4 | 5 | 6 |

Three or more items answered as “some”? Yes No

OR

Mean score of 2.0 or above? Yes No

Okay, now just four more questions:

[Circle the patient’s responses to the following questions:]

| | | |
|--|-----|----|
| • How long have you had this pain? (≥ 3 months?) | Yes | No |
| • Do you have access to a computer, tablet, or smartphone with internet capability? | Yes | No |
| • Do you have any problems reading English? | Yes | No |
| • Are you planning to start any other new studies for treating your pain or your tumors? | Yes | No |

- If not eligible: I’m sorry, but you are not eligible for the study because _____. However, if you are interested, I can provide you with some online resources about ACT that you can read on your own.
- If eligible: Okay, these initial screening questions suggest that you are eligible for the study. Now I’ll tell you a little more about it to see if you are interested.

IV) Procedures

- People who participate in this study will come to the NIH two to three times. The first time, you would come for about two days. During this visit:
 - Randomization – we will randomly assign people to the immediate intervention group or to the delayed intervention group.
 - All patients will:
 - Fill out questionnaires asking about pain, quality of life, emotional well-being
 - Get an electrocardiogram, or EKG – painless, to read heart rate
 - Immediate Intervention group –

- This group will stay and do four hours of ACT Training (two 2-hour sessions) with a psychologist or psychology associate.
- Delayed/Wait-list group –
 - Go home and do nothing different for two months, return for intervention after 8 weeks. During this time, if you were to start a new pain treatment or treatment study that might impact your level of pain, we would have to remove you from this study.

V) ACT Training

- You will learn some techniques that have been found effective for helping people deal with pain; ACT does not get rid of pain, it helps people change their relationship with their pain. In other words, instead of trying to fight your pain, we can talk about ways of living with your pain while focusing your energy on things that are most important to you. In this way, we try to help you have the best quality of life you can have, even while you have pain.
- You will continue to practice the ACT techniques at home:
 - Weekly emails – on an ACT-related topic with an assignment, something to practice during that week
 - Biweekly video chat sessions with a trainer to check on progress, continue to work on ACT techniques

VI) Follow-up

- All patients will return to the NIH after they complete the 8-week intervention:
 - Repeat questionnaires and EKG
- Final follow-up 6 months later from home
 - Repeat questionnaires from home computer
- To thank you for your time, we will be providing participants with a small amount of money each time they complete the follow-up questionnaires. We will also cover the costs of travel and some meals during your visits.

VII) Patient Interested?

Does this sound like something you would be interested in?

If no: Thank you for your time.

If yes: Okay, great! Let's try to find some possible dates when you could come for your first visit (ask about any upcoming surgeries that we may need to schedule around).

If eligible and interested, find possible dates for first visit:

Abbreviated Title: ACT Therapy for NF1Related Pain

Version Date: 02/19/2019

9.2 APPENDIX B: ADULT BACKGROUND INFORMATION FORM

Abbreviated Title: ACT Therapy for NF1Related Pain

Version Date: 02/19/2019

ADULT BACKGROUND INFORMATION FORM
(To be completed by adult participants at baseline)

Name: _____ Date: _____ Date of Birth: _____
 Phone Numbers: Home _____ Work _____ Cell _____
 Email: _____ Do you prefer: Skype Other: _____
 Facetime

Demographics

Sex: Male Female Race: White African American/Black
 Asian Native Hawaiian/Pacific Islander
 Unknown American Indian/Alaskan Native

 Ethnicity: Hispanic or Latino Not Hispanic or Latino
 Unknown

Marital Status: Single Married Divorced Separated Widowed

Occupational Status:

Are you currently working? No Yes On disability If working, hours per week: _____

Occupation: _____

How long at current job? _____

Are you currently in school (e.g., college, vocational school, taking a class)? No Yes

If yes, please specify: _____

Are you receiving/Did you receive any special educational accommodations? No Yes

Level of Independent Living:

- I take care of myself (i.e., cooking, cleaning, bathing, dressing) independently.
- I need some help taking care of myself.
- I live in residential care.
- Other (please specify: _____)

Educational History

Highest grade level in school completed (1 – 12): _____ years

Years of college completed (1 – 4): _____ years

Years of graduate/professional school completed: _____ years

School Performance: High School: Average Above Average Below Average
 College: Average Above Average Below Average Not applicable

Psychological/Neurological History

Have you been diagnosed with any of the following:

Attention Deficit: No Yes

Learning Disability: No Yes Specify type: _____

Depression: No Yes

Anxiety: No Yes

Other psychiatric diagnosis: No Yes Specify diagnosis: _____

9.3 APPENDIX C: ADULT PAIN QUESTIONNAIRE

(Self report form for 18+ years)

Pain Interference Index – Adult

Below you will find a list of questions about you and your pain. Please answer each question by circling a number between 0 and 6.

Please note that we are asking about your pain during the last week.

| Has your pain: | Not at all | | Some | | Completely | | |
|--|------------|---|------|---|------------|---|---|
| | | | | | | | |
| 1. made it difficult for you to do work (in or outside the home)? | 0 | 1 | 2 | 3 | 4 | 5 | 6 |
| 2. made it difficult for you to do activities outside of work (leisure activities)? | 0 | 1 | 2 | 3 | 4 | 5 | 6 |
| 3. made it difficult for you to spend time with friends and family members? | 0 | 1 | 2 | 3 | 4 | 5 | 6 |
| 4. affected your mood? | 0 | 1 | 2 | 3 | 4 | 5 | 6 |
| 5. affected your ability to do physical activities (like run, walk up stairs, play sports, do chores)? | 0 | 1 | 2 | 3 | 4 | 5 | 6 |
| 6. affected your sleep? | 0 | 1 | 2 | 3 | 4 | 5 | 6 |

Adapted by the Neurobehavioral Group, NCI (8/23/13)

9.4 APPENDIX D: PAIN INTERFERENCE –SHORT FORM 8A -ADULT

PROMIS Item Bank v1.0 – Pain Interference – Short Form 8a

Pain Interference – Short Form 8a

Please respond to each question or statement by marking one box per row.

| In the past 7 days... | | Not at all | A little bit | Somewhat | Quite a bit | Very much |
|------------------------------|--|--------------------------|--------------------------|--------------------------|--------------------------|--------------------------|
| 1 | How much did pain interfere with your day to day activities? |  |
| 2 | How much did pain interfere with work around the home?..... |  |
| 3 | How much did pain interfere with your ability to participate in social activities? |  |
| 4 | How much did pain interfere with your household chores?..... |  |
| 5 | How much did pain interfere with the things you usually do for fun? |  |
| 6 | How much did pain interfere with your enjoyment of social activities?..... |  |
| 7 | How much did pain interfere with your enjoyment of life? |  |
| 8 | How much did pain interfere with your family life?..... |  |

9.5 APPENDIX E: PAIN INTERFERENCE –SHORT FORM 8A –PEDIATRIC

PROMIS® Pediatric Item Bank v.1.0 - Pain Interference - Short Form 8a

Pediatric Pain Interference - Short Form

Please respond to each item by marking one box per row.

| In the past 7 days.... | | Never | Almost Never | Sometimes | Often | Almost Always |
|------------------------|---|--------------------------|--------------------------|--------------------------|--------------------------|--------------------------|
| | | 0 | 1 | 2 | 3 | 4 |
| 3793R1 | I had trouble sleeping when I had pain. |  |
| 1698bR1 | I felt angry when I had pain. |  |
| 2035R1 | I had trouble doing schoolwork when I had pain. |  |
| 9004 | It was hard for me to pay attention when I had pain. |  |
| 2045R1 | It was hard for me to run when I had pain. |  |
| 2049R1 | It was hard for me to walk one block when I had pain. |  |
| 1703R1 | It was hard to have fun when I had pain. |  |
| 2180R1 | It was hard to stay standing when I had pain. |  |

9.6 APPENDIX F: PEDSQL NEUROFIBROMATOSIS TYPE 1 MODULE

Neurofibromatosis Type 1: QOL instrument- Pediatric DIRECTIONS

This survey is for individuals with NF 1. Neurofibromatosis type 1 sometimes causes special problems. Please tell us **how much of a problem** each one has been for you during the **past ONE month** by circling:

- 0** if it is **never** a problem
- 1** if it is **almost never** a problem
- 2** if it is **sometimes** a problem
- 3** if it is **often** a problem
- 4** if it is **almost always** a problem

There are no right or wrong answers.

If you do not know an answer, take your best guess.

Thank you for your help!

In the past **ONE month**, how much of a **problem** has this been for you...

| PHYSICAL FUNCTIONING (problems with...) | Never | Almost never | Some- times | Often | Almost Always |
|--|--------------|----------------------------|---------------------------|--------------|-----------------------------|
| 1. Feeling physically weak | 0 | 1 | 2 | 3 | 3 |
| 2. Walking more than one block | 0 | 1 | 2 | 3 | 3 |
| 3. Climbing stairs | 0 | 1 | 2 | 3 | 3 |
| 4. Running | 0 | 1 | 2 | 3 | 3 |
| 5. Doing a sports activity or exercise | 0 | 1 | 2 | 3 | 3 |

| | | | | | |
|----------------------------------|---|---|---|---|---|
| 6. Lifting something heavy | 0 | 1 | 2 | 3 | 3 |
| 7. Doing chores around the house | 0 | 1 | 2 | 3 | 3 |

In the past **ONE month**, how much of a **problem** has this been for you...

| DAILY ACTIVITIES (problems with...) | Never | Almost Never | Some- times | Often | Almost Always |
|--|-------|-----------------|----------------|-------|------------------|
| 1. Putting on shoes | 0 | 1 | 2 | 3 | 4 |
| 2. Buttoning my shirt | 0 | 1 | 2 | 3 | 4 |
| 3. Combing my hair | 0 | 1 | 2 | 3 | 4 |
| 4. Getting into the bathroom to use the toilet | 0 | 1 | 2 | 3 | 4 |
| 5. Undressing to use the toilet | 0 | 1 | 2 | 3 | 4 |
| 6. Getting in and out of bathtub or shower | 0 | 1 | 2 | 3 | 4 |
| 7. Brushing my teeth | 0 | 1 | 2 | 3 | 4 |
| 8. Eating with a fork or knife | 0 | 1 | 2 | 3 | 4 |
| 9. Using a phone | 0 | 1 | 2 | 3 | 4 |
| 10. Shopping | 0 | 1 | 2 | 3 | 4 |
| 11. Managing money | 0 | 1 | 2 | 3 | 4 |
| 12. Driving | 0 | 1 | 2 | 3 | 4 |

Neurofibromatosis Type 1: QOL instrument- Adult

DIRECTIONS

This survey is for individuals with NF 1. Neurofibromatosis type 1 sometimes causes special problems. Please tell us **how much of a problem** each one has been for you during the **past ONE month** by circling:

- 0** if it is **never** a problem
- 1** is it is **almost never** a problem
- 2** if it is **sometimes** a problem
- 3** if it is **often** a problem
- 4** if it is **almost always** a problem

There are no right or wrong answers.

If you do not know an answer, take your best guess.

Thank you for your help!

In the past **ONE month**, how much of a **problem** has this been for you...

| PHYSICAL FUNCTIONING (problems with...) | Never | Almost never | Some- times | Often | Almost Always |
|--|--------------|-------------------------|------------------------|--------------|--------------------------|
| 1. Feeling physically weak | 0 | 1 | 2 | 3 | 3 |
| 2. Walking more than one block | 0 | 1 | 2 | 3 | 3 |
| 3. Climbing stairs | 0 | 1 | 2 | 3 | 3 |
| 4. Running | 0 | 1 | 2 | 3 | 3 |
| 5. Doing a sports activity or exercise | 0 | 1 | 2 | 3 | 3 |
| 6. Lifting something heavy | 0 | 1 | 2 | 3 | 3 |

| | | | | | |
|----------------------------------|---|---|---|---|---|
| 7. Doing chores around the house | 0 | 1 | 2 | 3 | 3 |
|----------------------------------|---|---|---|---|---|

In the past **ONE month**, how much of a **problem** has this been for you...

| DAILY ACTIVITIES (problems with...) | Never | Almost Never | Some- times | Often | Almost Always |
|--|-------|-----------------|----------------|-------|------------------|
| 1. Putting on shoes | 0 | 1 | 2 | 3 | 4 |
| 2. Buttoning my shirt | 0 | 1 | 2 | 3 | 4 |
| 3. Combing my hair | 0 | 1 | 2 | 3 | 4 |
| 4. Getting into the bathroom to use the toilet | 0 | 1 | 2 | 3 | 4 |
| 5. Undressing to use the toilet | 0 | 1 | 2 | 3 | 4 |
| 6. Getting in and out of bathtub or shower | 0 | 1 | 2 | 3 | 4 |
| 7. Brushing my teeth | 0 | 1 | 2 | 3 | 4 |
| 8. Eating with a fork or knife | 0 | 1 | 2 | 3 | 4 |
| 9. Using a phone | 0 | 1 | 2 | 3 | 4 |
| 10. Shopping | 0 | 1 | 2 | 3 | 4 |
| 11. Managing money | 0 | 1 | 2 | 3 | 4 |
| 12. Driving | 0 | 1 | 2 | 3 | 4 |

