3.3.1.2 Disease-specific Quality of Life

The PedsQL NF Module, Adult form is a questionnaire designed to assess various aspects of quality of life in individuals with NF1 (Nutakki, Hingtgen, Monahan, Varni, & Swigonski, 2013) ([Appendix F](#)). Items on this scale ask the respondent to indicate the extent to which they have had problems performing various activities over the past month, using a 0 – 4 Likert scale (0 = Never, 4 = Almost Always). The subscales that will be administered on this study include Physical Functioning (7 items) and Daily Activities (12 items). Mean scores for each subscale are linearly transformed to a 0-100 scale, and then can be compared to means and standard deviations of a normative group of patients with NF1. These two subscales should take less than five minutes to complete.

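### Appendix F prints the code 3 for both Often and Almost Always on every PedsQL NF1 Physical Functioning item, against the forms' own directions and Section 3.3.1.2

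*Combined protocol and SAP*

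**What the plan says.** Section 3.3.1.2 (Disease-specific Quality of Life) has respondents rate each item "using a 0 – 4 Likert scale (0 = Never, 4 = Almost Always"). It names two subscales, Physical Functioning with 7 items and Daily Activities with 12, and adds: "Mean scores for each subscale are linearly transformed to a 0-100 scale".

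Appendix F (Section 9.6) prints a pediatric and an adult form. The directions on each ask the respondent to circle a number and define the top one: "4 if it is almost always a problem".

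The Physical Functioning grid on each form then has five labelled columns, from Never to Almost Always, with the codes 0, 1, 2, 3, 3. The first pediatric row is "1. Feeling physically weak | 0 | 1 | 2 | 3 | 3" and the last adult row is "7. Doing chores around the house | 0 | 1 | 2 | 3 | 3". The Daily Activities grids print the full scale, for example "12. Driving | 0 | 1 | 2 | 3 | 4".

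Disease-specific quality of life is named in secondary objectives 1.1.2.1 and 1.1.2.2, and is covered by 1.1.2.3. Section 6.1 lists it as a between-group secondary endpoint.

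**The concern.** A respondent who follows the directions has no 4 to circle on any Physical Functioning item. If the printed numbers are what is stored or scored, an improvement from Almost Always to Often registers as no change. That happens at the most impaired end of the scale, in a trial that enrols people because pain interferes with their functioning. At stake is the sensitivity of one of the two subscales that carry the disease-specific quality-of-life endpoint.

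**Working it through.** **Step 1. Set the codes for Almost Always side by side.**

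| Place | Code |
|---|---|
| Section 3.3.1.2 | 4 |
| Directions, pediatric form | 4 |
| Directions, adult form | 4 |
| Daily Activities, both forms (2 × 12 = 24 rows) | 4 on all 24 |
| Physical Functioning, both forms (2 × 7 = 14 rows) | 3 on all 14 |

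Only the Physical Functioning grids disagree.

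**Step 2. Raw range.** With 7 items, the maximum sum is 7 × the top code.
- As stated in 3.3.1.2: 7 × 4 = 28, from 5 distinct codes.
- As printed: 7 × 3 = 21, from 4 distinct codes.

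**Step 3. Transformed range.** Score = (item mean ÷ 4) × 100.
- As stated: 4 ÷ 4 × 100 = 100, so the range is 0 to 100.
- As printed: 3 ÷ 4 × 100 = 75, so the range is 0 to 75. Section 3.3.1.2 does not say whether the score is reversed; if it is, the range is 25 to 100. Either way, 25 of 100 points at the impaired end cannot be reached.
- If the transform divides by the printed maximum of 3, the range is 0 to 100 again, but the tie remains and the score is on a different footing from one based on 4.

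**Step 4. Effect on change scores (transform based on 4).**
- Almost Always to Often on one item: (1 ÷ 7) ÷ 4 × 100 = 3.6 points as stated, 0 as printed.
- The same move on all seven items: 25 points as stated, 0 as printed.
- Almost Always to Sometimes on all seven: 50 points as stated, 25 as printed.

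**Step 5. Size under assumed answer patterns.** The documents give no response distribution, so these four are assumptions. Shares run from Never to Almost Always; values are for one item on the 0-100 scale, not reversed.

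| Assumed shares (%) | Mean, stated → printed | SD, stated → printed | SD ratio |
|---|---|---|---|
| 30/25/25/15/5 | 35.0 → 33.75 | 30.0 → 27.7 | 0.92 |
| 20/20/20/20/20 | 50.0 → 45.0 | 35.36 → 29.15 | 0.82 |
| 10/15/25/25/25 | 60.0 → 53.75 | 32.02 → 25.34 | 0.79 |
| 5/10/20/25/40 | 71.25 → 61.25 | 29.87 → 21.61 | 0.72 |

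The mean shifts by 25 × the share answering Almost Always, which is 1.25 to 10 points here. Because the SD shrinks along with the differences, the loss in standardized effect cannot be sized from the documents.

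**The case against.** **It may be a fault in reading the PDF.** Other scale grids in the available text are damaged. The PASS-20 directions run from 0 to 5, yet all 20 rows stop at 4, and three rows of the Appendix A screening grid lose a digit. Damage can therefore be uniform and confined to the last column of one grid. The two Physical Functioning grids also carry the same items, so one may be a copy of the other and the 14 rows are not 14 independent confirmations. This stands in part, and only the original form settles it. A reading fault is still the less likely explanation. The damaged grids lose cells, whereas these keep all five columns and carry a wrong digit. The repeated 3 also appears in four separate table fragments, because the pediatric grid breaks after item 5 and the adult grid after item 6.

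**The printed numbers may never be used.** Section 4.1 says that all questionnaires are given on a computer or tablet, and the stored codes are not shown. Often and Almost Always sit in separate labelled columns, so the answers can be told apart if the label or position is kept. This stands fully. A reader might infer from Appendix F that the quality-of-life data are compressed; the documents do not show that.

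**Comparison with norms.** A reader might also infer that a planned comparison with NF1 norms is broken. Section 3.3.1.2 says only that such a comparison is possible, and Section 6.1 plans none.

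**Limited reach.** Any tie would apply to both arms alike, so the plausible harm is lost sensitivity on one subscale of a secondary endpoint. That also stands, and it is why the severity is low.

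**Conclusion.** Wrong as written, low severity. The grid contradicts the directions above it and the scale in the protocol body, and the governing text is clear that the top code is 4.

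The loss of scale range is conditional. It requires that data are captured or scored from the printed numerals, and the quarter-range figure further assumes a transform based on a maximum of 4. If the electronic form already stores 4, or scoring uses the label, the finding reduces to a misprint in an appendix. The primary endpoint (Pain Interference Index), its test and the sample size are unaffected in either case.

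**What to change.** 1. In Appendix F, change the last Physical Functioning column to 4 on all 14 rows, after a look at the original form to confirm the misprint.
2. Check which value the deployed electronic form stores for Almost Always on these seven items, in each version in use.
3. If both options were stored as 3, recode from the response label or box position. Where only the numeral was kept, the two answers cannot be separated, and the number of affected records should be reported with the subscale results.

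Section 3.3.1.2 already gives the right scale and needs no change. The cost is one correction to the appendix and one check of the form; recoding arises only if the check finds the printed codes in use.
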